### 4. Study Design

We will use the design of factorial parallel randomized controlled trial to conduct these two studies in the same patient group. A computer-generated list of randomizations (Research Randomizer, [www.randomizer.org](http://www.randomizer.org)) will be used for these group allocations. We will use stratified randomization method to ensure random allocations of these two treatments (spectral entropy and ProAQT goal-directed therapy) in all patients. Allocation will be concealed with sequentially numbered sealed opaque envelopes. The principal investigator will open the respective concealed envelope containing the patient allocation to the treatment arm on the day of surgery immediately before induction of anesthesia. In this trial, we will conform to the recommendations in the Consolidated Standards of Reporting Trials (CONSORT) statement. In addition, we will follow the principle of intention-to-treat in our analyses of the trial results.

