## 1. Introduction

Patients undergoing thoracotomy in thoracic surgery are prone to have complications of delayed recovery from general anesthesia and perioperative instable hemodynamics due to the relatively invasive procedures and patient's underlying morbidity. Therefore, intraoperative monitoring and corresponding management are of great importance to prevent relevant complications in thoracic surgery. This study aims to investigate the clinical benefits of two intraoperative monitoring techniques in patients undergoing thoracotomy surgery, including depth of anesthesia and minimally invasive cardiac output monitoring. First, M-Entropy system will be used to measure the depth of anesthesia and be evaluated regarding the effect of spectral entropy guidance on postoperative recovery. Second, we will apply ProAQT device in guiding goal-directed hemodynamic therapy and assess its impact on occurrence of postoperative pulmonary complications and recovery. In this study, we will conduct a factorial parallel randomized controlled trial and use the method of stratified randomization to evaluate both two monitoring technologies in the same patient group. The results of this study will provide important evidence and clinical implication for precision anesthesia and enhanced recovery after surgery (ERAS) protocol in thoracic surgery.

This study aims to investigate the clinical benefits of two intraoperative monitoring techniques in patients undergoing thoracotomy surgery, including M-Entropy system and ProAQT sensor, as follows:

- 1) To evaluate the effect of M-Entropy guidance on the emergence from anesthesia and risk of postoperative delirium.
- 2) To apply ProAQT in guiding goal-directed hemodynamic therapy and assess its impact on postoperative pulmonary complications and recovery.

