### 3. Criteria of Eligibility

We will enroll the patients undergoing video-assisted thoracotomy at Shuang Ho Hospital, Taipei Medical University, New Taipei City, Taiwan. Exclusion criteria will be age < 20 years, pregnancy, end-stage renal disease, emergency surgery, presence of circulatory shock needing vasoactive drugs before surgery, any diagnosis of aortic diseases, cerebral vascular diseases or trauma, and high-degree cardiac arrhythmia (e.g. atrial fibrillation), uses of cardiac pacemaker or automated implantable cardioverter defibrillator, New York Heart Association functional classification 4, long-term use of psychiatric medications, intraoperative blood loss > 1 L, intraoperative blood transfusion, planned or unanticipated transfer to intensive care unit for postoperative mechanical ventilation, and patient refusal to participate.

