### ***Statistical Analysis***

The distributions of baseline patient characteristics and outcome variables will be compared between two groups using chi-square tests or Fisher's exact test for categorical variables and either t tests or Wilcoxon rank sum tests for continuous variables, as appropriate. For time to event data, Kaplan-Meier method and log-rank test will be applied for group comparisons. Multivariable logistic regression, simple linear regression, or Cox proportional hazards regression analyses will be used to identify potential influential factors of outcomes of interest. A two-sided significance level of 0.05 was used to define statistically significant difference. All the statistical analyses will be conducted using Statistics Analysis System (SAS), Version 9.4 (SAS Institute Inc., Cary, NC, USA).

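### The randomisation is called stratified but names no baseline factor, and no adjusted treatment effect is pre-specified, so extent of surgery is controlled in neither allocation nor analysis

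*Combined protocol and SAP*

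**What the plan says.** **Allocation.** Section 4 (Study Design) sets up a factorial trial: "We will use the design of factorial parallel randomized controlled trial to conduct these two studies in the same patient group". The allocation source is "A computer-generated list of randomizations (Research Randomizer", an online tool, and the stratification sentence reads: "We will use stratified randomization method to ensure random allocations of these two treatments (spectral entropy and ProAQT goal-directed therapy) in all patients". The reference attached to that sentence is a methods paper on stratified randomisation. The section gives no stratum, allocation ratio or block size. Envelopes are opened just before anaesthesia is induced.

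**Who enters.** Section 3 (Criteria of Eligibility) states: "We will enroll the patients undergoing video-assisted thoracotomy at Shuang Ho Hospital". The exclusions cover emergency surgery, trauma, shock, severe heart failure and other conditions. They also cover "intraoperative blood loss > 1 L, intraoperative blood transfusion, planned or unanticipated transfer to intensive care unit for postoperative mechanical ventilation". None refers to type of procedure or extent of resection.

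**What drives risk.** Section 1 (Introduction) attributes delayed recovery and unstable haemodynamics to two sources together: "due to the relatively invasive procedures and patient's underlying morbidity". The Background subsection on enhanced recovery repeats this.

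**Analysis.** The Statistical Analysis section plans unadjusted two-group tests and, in addition: "For time to event data, Kaplan-Meier method and log-rank test will be applied for group comparisons". Its regression models "will be used to identify potential influential factors of outcomes of interest". No covariate is listed, and no model is designated as the source of the treatment effect.

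**The concern.** A reader told that randomisation was stratified, with a methods reference, will assume that at least one important baseline factor was balanced by design. The text does not support that assumption. If the two treatments are the only strata, the procedure balances the numbers in the four cells and nothing about the patients.

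Extent of surgery is an obvious candidate factor. Eligibility leaves it open, the documents themselves link invasiveness to delayed recovery and haemodynamic instability, and the planned operation would ordinarily be known when the envelope is opened. It could plausibly affect both primary outcomes: time to eye opening for the entropy comparison and pulmonary complications for the ProAQT comparison. Baseline imbalance in a factor can be handled in allocation or in analysis, and here neither is specified. At stake are a misleading description of the method and some precision that could be gained cheaply.

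**Working it through.** The plan gives no sample size, event rate, standard deviation or case mix, so there is no planned figure to reproduce. All inputs below are assumptions chosen to show the order of magnitude.

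**1. Size of chance imbalance.** Let q be the share of patients having the more extensive procedure and N the total randomised, with half at each level of a treatment factor. Under simple 1:1 allocation the between-arm difference in that share has SD = sqrt(4q(1−q)/N). For q between 20% and 50%, the chance of an imbalance of at least 10 percentage points is:

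| N | Chance of ≥10-point imbalance |
|---|---|
| 60 | 33–44% |
| 100 | 21–32% |
| 200 | 8–16% |
| 300 | 3–8% |

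Blocked allocation within strata of that factor would bring this close to zero.

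**2. Effect on the complication comparison.** Assume q = 50% and complication risks of 30% (more extensive) and 10% (less extensive). Let n = N/2 be the number per level of a factor.

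- Overall risk: 0.5×0.30 + 0.5×0.10 = 0.20. Total variance: 0.20×0.80 = 0.16.
- Variance within procedure groups: 0.5×0.30×0.70 + 0.5×0.10×0.90 = 0.15.
- Share explained by procedure: (0.16 − 0.15)/0.16 = 6%.
- 95% range of the shift in risk difference due to imbalance: 1.96 × sqrt(2×0.25/n) × 0.20.
- 95% half-width of the risk difference: 1.96 × sqrt(2×0.16/n) without control, and 1.96 × sqrt(2×0.15/n) with full control.

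| n per level | Shift from imbalance | Half-width, no control | Half-width, full control |
|---|---|---|---|
| 50 | ±3.9 points | ±15.7 | ±15.2 |
| 100 | ±2.8 points | ±11.1 | ±10.7 |
| 150 | ±2.3 points | ±9.1 | ±8.8 |

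The shift is a component of the ordinary interval and does not add to it: at n = 100, sqrt(10.7² + 2.8²) = 11.1. The narrowing is 1 − sqrt(0.15/0.16) = 3% at every n.

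**3. Sensitivity.** With risks of 20% v 5% and q = 50%, total variance is 0.125×0.875 = 0.1094 and the between-group part is 0.075² = 0.0056, or 5%; the narrowing is 1 − sqrt(1 − 0.0056/0.1094) = 2.6%. With 30% v 10% and q = 20%, the figures are 0.14×0.86 = 0.1204 and 0.2×0.8×0.20² = 0.0064, again 5%; the narrowing is 2.7%.

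**4. Time to eye opening.** The documents give nothing on its spread or its relation to procedure. As a generic illustration for a continuous outcome with a standardised effect of 0.5, 63 per arm gives 80% power unadjusted. If procedure explained 10%, 20% or 30% of the variance, an adjusted analysis would need 57, 51 or 44 per arm, and an unadjusted test at those sizes would have 76%, 71% or 65% power. Nothing in the documents says which of these values, if any, applies.

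**The case against.** The strongest reply is that not stratifying by a prognostic factor is an accepted choice. Randomisation keeps the comparison unbiased in expectation and the test valid, and the ±2.8-point shift at n = 100 already lies inside the ±11.1-point interval. All of that stands, and it limits the point to transparency and a modest gain in precision.

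Several stronger readings are tempting but unsupported:

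- *Randomisation is stratified by the two treatments and nothing else.* The Study Design section never states what the strata are. This is the natural reading of the sentence, but the firm fact is that no baseline factor is named.
- *Every video-assisted procedure is eligible.* Entry is limited to video-assisted thoracotomy at one hospital, with a long list of exclusions. The blood-loss, transfusion and intensive-care exclusions also trim the most complicated cases, although apart from a planned transfer they cannot act before the envelope is opened.
- *Extent of surgery is the main source of case-mix variation.* The documents name invasiveness and underlying morbidity together, without ranking them.

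For emergence time, the Study Methods section times the end of anaesthesia in all patients to favour early waking after closure. That may weaken any route through length of anaesthesia.

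It can also be said that the plan includes multivariable regression. But its stated purpose is to find influential factors, so it does not define an adjusted treatment effect.

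**Conclusion.** The point holds as a minor one. The plan calls its randomisation stratified without naming a baseline factor. It leaves procedure extent open at entry while citing invasiveness as a source of risk, and it pre-specifies no adjustment. A reader might infer that the results would be biased or the tests invalid; neither follows.

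The cost is avoidable chance imbalance, which shrinks as N grows, and some lost precision. For pulmonary complications, under the assumed risks and case mixes, procedure explains about 5–6% of outcome variance, and full control narrows the interval by about 3%. For time to eye opening the gain may be smaller or larger and cannot be computed from the documents. These figures would change with the true case mix, event rates and sample size.

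**What to change.** **If recruitment has not started.** In Study Design, replace the stratification sentence with text to this effect: patients will be allocated 1:1:1:1 to the four treatment combinations in permuted blocks of varying size, stratified by planned procedure extent (two categories defined in the protocol), recorded before the envelope is opened. In Statistical Analysis, state that both primary comparisons will be adjusted for, or stratified by, that factor, and name the effect measure. Both changes are needed: if allocation is stratified but the analysis ignores the strata, the standard error does not reflect the balance achieved.

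**If recruitment has started.** Keep the existing list, describe the allocation as being to the four factorial cells only (if that is how the list was built), and make the pre-specified adjustment alone, fixed before outcomes are examined by group.

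**Cost.** Two envelope series to prepare and handle, and a stratum that must be defined and recorded before allocation. The analysis-only route needs just the definition, the recorded planned procedure and a sentence in the plan.

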### 5. Study Methods

#### **The effect of M-Entropy guidance of anesthesia depth on postoperative recovery: A single-blind randomized controlled trial**

Standard monitoring will be applied, including five-lead electrocardiogram, pulse oximetry, capnography, radial artery catheterization for arterial blood pressure, and internal jugular vein cannulation for central venous pressure. Patients will be given balanced general anesthesia, including fentanyl 1–2  $\mu\text{g}\cdot\text{kg}^{-1}$  and propofol 1–2  $\text{mg}\cdot\text{kg}^{-1}$  for induction, and rocuronium 0.8  $\text{mg}\cdot\text{kg}^{-1}$  to facilitate tracheal intubation. Anesthesia will be maintained using sevoflurane 2–3 vol% in oxygen. An additional bolus of intravenous fentanyl 50  $\mu\text{g}$  will be administered before surgical incision. Pressure-controlled ventilation with a positive end expiratory pressure of 5 cm  $\text{H}_2\text{O}$  and peak pressure < 30 cm  $\text{H}_2\text{O}$  will be applied for both double-lung ventilation and OLV. OLV will be initiated after patients are in the lateral decubitus position. During double-lung ventilation the inspiratory oxygen fraction will be set to 0.6, whereas 0.8–1.0 will be used for OLV to ensure oxygen saturation higher than 92%. For double-lung ventilation, tidal volumes up to 8  $\text{ml}\cdot\text{kg}^{-1}$  and a respiratory rate of 10–15  $\text{min}^{-1}$  will be chosen, for OLV tidal volumes up to 6–7  $\text{ml}\cdot\text{kg}^{-1}$  with a respiratory frequency of 10–15  $\text{min}^{-1}$  will be used. In both groups re-inflating of the previously non-ventilated lung will be restarted by a manual recruitment maneuver with peak pressure 30 cm  $\text{H}_2\text{O}$  for 10 s three times. Intravenous parecoxib 40 mg will be given promptly after induction of anesthesia, followed by parecoxib 20 to 40 mg every 12 hours for three days.

Intravenous as-needed analgesia with morphine and/or ketorolac will be used to relieve breakthrough pain, which will be switched to oral diclofenac on the postoperative 2nd or 3rd day.

In the M-Entropy group, dosage of volatile anesthetics will be adjusted to achieve the response and state entropy values between 40 and 60 from the start of anesthesia to the end of surgery. In the control group, dosage of volatile anesthetics will be titrated according to clinical judgment. This will be to maintain mean arterial pressure and heart rate within 20% range of the baseline. In case of signs of inadequate anesthesia (e.g. movement, cough and swallowing), anesthetic dose will be increased. M-Entropy monitoring will be continued in the control group, but the entropy number and EEG waveform will be concealed from the anesthetist in charge. Entropy values, hemodynamic, and expiratory gas data will be recorded in 5-min intervals. In all patients, cessation of general anesthesia will be timed to facilitate early awakening after wound closure. After reversal of the neuromuscular blocking agent and response to verbal command, all subjects will be extubated at the operating room and then transferred to the postanesthetic care unit. In the postoperative period, surgeons, medical and nursing staff at the postanesthetic care unit will be blinded to group allocation.

Primary outcome is time to spontaneous eye opening. Secondary outcomes include time to tracheal extubation, time to orientation in time and place, time to leave operating room, and events of emergence agitation, postoperative delirium, and intraoperative recall or awareness. We will use the Richmond Agitation-Sedation Scale to evaluate the level of agitation and sedation promptly after extubation. Events of delirium will be evaluated using the Confusion Assessment Method at the postanesthetic care unit 30 minutes after tracheal extubation. An independent adjudicator blinded to the group allocation will measure all the outcomes.

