### ***Anesthesia depth monitoring using spectral entropy***

Meta-analysis has showed that bispectral index (BIS)-guided anesthesia may enhance early recovery time in patients undergoing surgery with general anesthesia compared to clinical signs. However, compared with BIS, M-Entropy™ system (GE Healthcare, Helsinki, Finland) is much less investigated regarding its clinical effectiveness. The use of entropy to track the anesthetic state of patients is a relatively new monitoring approach. Entropy measures the degree of disorder or the lack of synchrony or consistency in a system. Entropy-based analyses have been applied to the EEG and used to construct EEG-based indices meant to indicate the depth of anesthesia. Although EEG-based monitoring of anesthesia depth is widely used and effective in maintaining the optimal range of anesthesia depth in total intravenous anesthesia, there is sparse evidence regarding the role of spectral entropy monitoring in volatile anesthesia regarding time to emergence from anesthesia as well as reduction in anesthetic agent use. Besides, whether entropy guidance in general anesthesia protects against development of postoperative delirium remains unclear in thoracic surgery.

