The primary outcome is in-hospital postoperative pulmonary complication, including atelectasis, pleural effusion, pneumonia, empyema, pulmonary embolism, re-operation, and respiratory failure. The diagnosis of atelectasis and pleural effusion will be made based on routinely performed chest radiographs on postoperative days 1 and 3. Pneumonia will be diagnosed if a patient presents with fever, leukocytosis and new infiltrates on chest radiography. Pleural empyema and pulmonary embolism will be confirmed by spiral computed tomography scan. Respiratory failure is defined as described. Secondary outcomes include relative change of PaO2/FiO2, PaO2/FiO2 values after induction of anesthesia and at the end of surgery, acute kidney injury (defined by Acute Kidney Injury Network Criteria), cardiac complications (myocardial infarction diagnosed by electrocardiogram and troponin T serum concentration; newly developed atrial fibrillation), clinically relevant hypotensive episodes (decrease in mean arterial pressure > 20% for more than 15 min requiring vasopressors), newly developed stroke, and length of hospital stay. All outcomes will be determined again 30 days after surgery and documented by research staff blinded to group allocation.

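### Does a single delirium reading 30 minutes after extubation fall short of the aim on postoperative delirium?

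*Combined protocol and SAP*

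**What the plan says.** The Introduction states the first aim as "To evaluate the effect of M-Entropy guidance on the emergence from anesthesia and risk of postoperative delirium". No period is attached to the delirium part. The Background subsection on anesthesia depth monitoring gives the motivation: it says that "whether entropy guidance in general anesthesia protects against development of postoperative delirium remains unclear in thoracic surgery".

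The M-Entropy part of Study Methods names time to spontaneous eye opening as the primary outcome. Its secondary outcomes include three recovery times and "events of emergence agitation, postoperative delirium, and intraoperative recall or awareness". Two sentences after that list, in the same paragraph, the delirium measurement is defined: "Events of delirium will be evaluated using the Confusion Assessment Method at the postanesthetic care unit 30 minutes after tracheal extubation". The paragraph ends by assigning all outcome measurement to an independent adjudicator who does not know the allocation. No other delirium assessment is described for the M-Entropy comparison.

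The ProAQT part of Study Methods does put a window in an outcome's name: "The primary outcome is in-hospital postoperative pulmonary complication". It closes with a sentence saying that all outcomes are determined again at 30 days. The outcomes listed there do not include delirium.

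**The concern.** The words risk and development normally describe whether an event occurs over a period. A single assessment gives something narrower: the proportion of patients who are positive at one moment. A patient who is clear at 30 minutes and becomes delirious that evening or the next day counts as free of delirium.

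If the aim is read as covering the hospital stay, two wrong conclusions are possible. A null result at 30 minutes could be reported as no protection against postoperative delirium, and a difference could be reported as protection lasting beyond the recovery unit. Neither would be supported. Delirium is one of only two effects named in the aim, and the Introduction expects the results to inform enhanced-recovery practice, so an over-wide claim could travel. The methods also list emergence agitation and delirium as separate events, which can suggest that delirium was meant as something beyond emergence.

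**Working it through.** The documents give no delirium rate, effect size or power for this outcome, so there is no planned figure to reproduce. The check compares the relevant texts and sets out what the reading estimates.

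**1. Is the outcome defined well enough to analyse?** The M-Entropy methods give the instrument (Confusion Assessment Method), the place (recovery unit), the time (30 minutes after extubation) and the assessor (independent and blinded). Each patient yields one binary result. The Statistical Analysis section provides chi-square or Fisher's exact tests for categorical variables. Nothing is left for the analyst to invent.

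**2. How many statements really lack a window?**
- Introduction, first aim: no window.
- Background: a remark about a gap in existing evidence, not an outcome definition.
- M-Entropy outcome list: the time follows two sentences later in the same paragraph, so this mention does have a window.

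That leaves one, the aim.

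**3. Do other parts of the plan imply delirium follow-up over several days?**
- The later days mentioned in the M-Entropy section, "which will be switched to oral diclofenac on the postoperative 2nd or 3rd day", belong to the pain-relief regimen and imply no delirium window.
- The exclusion for "planned or unanticipated transfer to intensive care unit for postoperative mechanical ventilation" and the statement that "all subjects will be extubated at the operating room and then transferred to the postanesthetic care unit" determine who is assessed, not when delirium is read.
- The 30-day sentence ends the ProAQT outcomes paragraph. Read in place, it covers those outcomes. It names no delirium instrument.

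None of these makes the aim a promise about the whole stay. The aim itself pairs delirium with emergence. The other M-Entropy outcomes also concern emergence or early recovery, except intraoperative recall or awareness, for which no assessment time is given.

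**4. What does the reading estimate, and what would rewording alter?** For group *g* (M-Entropy = 1, control = 0), let *p_g* be the proportion positive at 30 minutes. Let *l_g* be the proportion negative at 30 minutes but delirious at some other time in a wider window. The risk over that window is

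*R_g* = *p_g* + *l_g*,

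and the group difference is

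*R_1* − *R_0* = (*p_1* − *p_0*) + (*l_1* − *l_0*).

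The plan estimates the first bracket, and randomisation with blinded assessment makes that a fair comparison. The second bracket is not observed, and the documents give no value for any of these terms.

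Renaming the outcome and narrowing the aim leaves *p_1* − *p_0*, its test and its data exactly as they are. Only further assessments would supply *l_1* − *l_0*.

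**The case for a change.** The strongest case for a change is that a complete definition does not by itself make the measurement match the aim. The plan shows elsewhere that it can name a window, as with the in-hospital ProAQT primary outcome. Patients remain under observation after the recovery unit, with chest radiographs on postoperative days 1 and 3. Rewording one aim and one outcome name would cost nothing in data collection and would guard against an over-wide claim. The 30-day sentence could also be misread as reaching the M-Entropy outcomes.

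Part of this stands. The aim has no window, and the reading does not support inference about delirium later in the stay. A sponsor amending the text for other reasons could word the aim to match the measurement and state that the 30-day determination concerns the ProAQT outcomes.

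The rest is weaker. A general term in an aim that the methods then make specific is ordinary protocol structure. Half an hour after extubation is itself postoperative, so label and measurement do not contradict each other. It also goes too far to say that the reading cannot address the aim: a randomised difference at 30 minutes is direct evidence on early postoperative delirium. Only extrapolation beyond that point is unsupported, and the stated assessment time lets any reader see the limit. On the 30-day sentence, even the wider reading would leave the period between 30 minutes and 30 days without a specified assessment, so it does not alter the argument.

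**Conclusion.** The observation is accurate, but no change to the plan follows, because the change would bring no gain. One aim lacks a time window; the outcome it refers to is secondary and is fully defined in the methods. Followed as written, the plan gives a valid comparison of delirium between randomised groups at the stated time. Rewording would alter no measurement, analysis, number or result. Adding later readings would answer a different and wider question at the cost of extra assessments, and nothing in the documents commits the trial to that question.

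This rests on two readings of the text: that the M-Entropy methods paragraph governs what delirium means in the trial, and that the 30-day sentence belongs to the ProAQT outcomes. It does not rest on any assumption about how common late delirium is, since the documents give no such figure. What remains is a point for reporting: any conclusion on delirium, positive or null, should be stated for the recovery unit at 30 minutes after extubation.
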